## 11.4 Adverse Events of Special Interest

The AESIs are:

- TEE –Embolic and thrombotic events (Standardized MedDRA Query [SMQ]);
- Bleeding events –Haemorrhages (SMQ);
- Anaphylactic reaction–Anaphylactic reaction (SMQ)(broad).

Summaries by SOC and PT for each AESI will be provided separately.

In addition, AESIs will be listed separately in the format specified in Section 11.3.

CSL will provide PCI with the MedDRA SMQs.

## 11.5 Deaths and Serious Adverse Events

There will be an entry in the overall summary table showing the number of subjects with treatment-emergent SAEs and the number of events. Another entry will show the number of treatment-emergent deaths. Treatment-emergent SAEs and deaths will be differentiated for caused by COVID-19.

An overview summary of treatment-emergent SAEs, including counts and percentages of subjects as well as the number of events, will be provided for:

- any treatment-emergent SAE;
- treatment-emergent SAEs caused by COVID-19;
- any treatment-emergent death;
- treatment-emergent death caused by COVID-19;
- treatment-emergent SAEs occurring within 24 hours of investigational product administration;
- Relates treatment-emergent SAEs;
- treatment-emergent SAEs leading to study discontinuation;
- treatment-emergent SAEs leading to study discontinuation caused by COVID-19;
- treatment-emergent SAEs in each intensity category;
- treatment-emergent SAEs in each outcome category;
- treatment-emergent SAEs not resolved or resolved with sequelae caused by COVID-19.

For treatment-emergent SAEs a summary table by SOC and PT as specified in Section 11.3 will be provided.

Deaths will be listed for all available data. An additional by-subject listing for SAEs (including deaths) will be produced for all available data which will contain the information as specified in Section 7 and in addition information for criteria for SAE, hospitalization admission and discharge date, alternative cause for SAE not related to study treatment. SAEs and deaths caused by COVID-19 will be flagged.

### **11.6 Adverse Events Leading to Discontinuation of Study Treatment, Withdrawal from the Study, and Other Significant Adverse Events**

For AEs leading to study discontinuation, a summary table by SOC and PT as specified in Section 11.3 will be provided. AEs leading to study discontinuation will also be listed. AEs leading to study discontinuation caused by COVID-19 will be flagged and displayed separately.

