4.2 Discontinuation of Treatment and / or Subject Withdrawal

4.2.1 Reasons for Discontinuation of Treatment and / or Subject Withdrawal

Subjects may discontinue treatment with investigational product or withdraw from the study at any time at their own request, or at the discretion of the investigator or CSL for safety, behavioral or administrative reasons (eg, due to an AE, protocol deviation, loss to follow-up, subject noncompliance, study terminated by CSL).

In accordance with International Conference on Harmonization (ICH) principles of Good Clinical Practice (GCP), the investigator always has the option to advise a subject to withdraw from the study if the subject's safety or well-being is compromised by his or her further participation in the study. Concern for the interests of the subject must always prevail over the interests of the study.

The investigator should record in the electronic case report form (eCRF) and in the subject's medical records the reason and date of subject withdrawal or discontinuation of treatment with investigational product.

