7.1 Contraindications and Precautions to Further Dosing

The following are considered contraindications for further administration of the investigational product for an individual subject:

- Anaphylaxis or severe and clinically significant allergic reaction that is causally related to the investigational product active substance or excipients.
- A diagnosis of a TEE (other than superficial thrombophlebitis and catheter-related thromboses), irrespective of causal relationship to the investigational product.
- A clinically significant, abnormal bleeding event, irrespective of causal relationship to the investigational product.
- The subject has been administered a prohibited therapy or has a prohibited change in concomitant therapy, at the discretion of the investigator in consultation with CSL.
- Any event that is considered by the investigator and / or CSL to be serious and clinically significant, and that would suggest significant hazard to the subject following further administration of the investigational product.

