10.3.3 Safety Analyses

AEs with a start date and time on or after the first injection date and time of investigational product are considered treatment-emergent AEs. AEs with missing or partial start date or time will also be considered treatment-emergent following the worst case principle, unless the partial date clearly indicates that the AE started before first injection date and time.

Adverse events with a start date occurring after administration of IV investigational product and occurring before the first administration of SC investigational product will be analyzed separately from AEs with a start date occurring after the first administration of SC investigational product.

Only treatment-emergent AEs will be included in analyses, although all AEs will be listed. The following tables will be presented for AEs occurring at any dose:

- Summary of subjects with AEs (number with any AE, with AEs occurring within 24 hours of investigational product injection, with SAE, with related AE, with AEs leading to study discontinuation, with each intensity, and with each outcome).

- Summary of subjects with SAEs (number with any SAE, with SAEs occurring within 24 hours of investigational product injection, with related SAE, with SAEs leading to study discontinuation, with each intensity, and with each outcome).
- Incidence of subjects with AEs by system organ class (SOC) and preferred term.
- Incidence of subjects with SAEs by SOC and preferred term.
- Incidence of subjects with AEs by severity and SOC and preferred term.
- Incidence of subjects with AEs by relationship to investigational product and SOC and preferred term.
- Incidence of subjects with AEs leading to discontinuation by SOC and preferred term.
- Incidence of subjects with TEEs by SOC and preferred term.
- Incidence of subjects with bleeding events by SOC and preferred term.
- Incidence of subjects with anaphylaxis by SOC and preferred term.
- The number of subjects experiencing AEs which occur in at least 1 treatment in at least 1, 2, 3, 4 and 5% of events will also be presented.

Summaries will include the number and percentage of subjects, the number of AEs, and the number of AEs per injection and per subject year (where applicable).

A summary of non-serious AEs only will be presented by treatment and also by SOC, preferred term, and treatment.

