The tables referring to TEAEs on or after first SC injection will comprise two parts: one – indicated in the numbering by x.1 – containing the number of subjects, percentage of subjects, and number of events, and the other – indicated in the numbering by x.2 – containing the event rates per administration and per subject year. The tables referring to TEAEs on or after the IV loading dose and before the first SC injection will comprise only the first part (number and percentage of subjects and number of events) as described above and no rates.

AE rates per SC injection for each safety evaluation period will be calculated as follows:

- AE Rate per SC Injection =  $\frac{\text{Number of events for a particular PT}}{\text{Number of SC injections}}$

where number of SC injections will be the sum of the SC injections that subjects received during the respective safety evaluation period.

- AE Rate per Subject SC Year =  $\frac{\text{Number of events for a particular PT}}{\text{Subject SC years}}$

where subject SC years will be the sum of the time in years that subjects were exposed to study treatment administered by SC injections during the respective safety evaluation period (sum of the duration after SC injections of the respective safety evaluation period in years).

The safety evaluation periods (Treatment Period 1, Treatment Period 2, and overall) are defined for the Safety analysis in Section 8.2.8.

For TEAEs which started on or after the IV loading dose but before the first SC dose, a summary table as described below will be provided and a table of TEAEs by SOC and PT as described below.

An overview summary of TEAEs will be provided as specified in Section 7 for:

- Any TEAE;
- Any SAEs;
- Any SAEs caused by COVID-19;
- Any deaths;

- Any deaths caused by COVID-19;
- TEAEs occurring within 24 hours of investigational product administration;
- Relates TEAEs;
- TEAEs leading to study discontinuation;
- TEAEs leading to study discontinuation caused by COVID-19;
- TEAEs in each intensity category;
- TEAEs in each outcome category;
- TEAEs not resolved or resolved with sequelae caused by COVID-19.

The following summary tables will be provided as specified in Section 7 for:

- TEAEs by SOC and PT;
- TEAEs by intensity, SOC, and PT;
- Related TEAEs by SOC and PT;
- TEAEs leading to study discontinuation by SOC and PT;
- Non-serious TEAEs by SOC and PT;
- Laboratory Findings reported as AEs.

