The relationship between MedDRA SOC, PT, and Verbatim Text will be listed.

TEAEs will be listed for the Safety population. AEs without specification for treatment-emergency will be listed for all data available. The listings will include the variables as specified in Section 7 and in addition MedDRA SOC, PT, and the verbatim, AE start and end date and time if available, duration of AE in days, intensity, serious (yes or no), relationship to treatment (yes or no), outcome, action taken, and AE flags (TEAE, SAE, temporal relationship within 24 hours, laboratory finding, AESI).

The following listings will be provided:

- Non-TEAEs – all data available;
- TEAEs on or after IV loading dose and before first SC dose – Safety population;
- TEAEs on or after first SC dose – Safety population;
- AEs related to laboratory findings – all data available;
- AEs caused by COVID-19;
- MedDRA SOC and PT with all AE verbatim – all data available.

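### SAP 11.6 is headed to cover adverse events that stop study treatment, but every discontinuation output counts only leaving the study

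*SAP*

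**What the plan says.** The heading of SAP 11.6 is "Adverse Events Leading to Discontinuation of Study Treatment, Withdrawal from the Study, and Other Significant Adverse Events". The text beneath it plans a table ("For AEs leading to study discontinuation, a summary table by SOC and PT as specified in Section 11.3 will be provided") and a listing ("AEs leading to study discontinuation will also be listed"), with COVID-19 cases flagged. SAP 11.3 names the same table as "TEAEs leading to study discontinuation by SOC and PT".

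Protocol 4.2.1 sets out two possibilities: "Subjects may discontinue treatment with investigational product or withdraw from the study at any time at their own request". It asks the investigator to record the reason and date of either one in the eCRF and the medical record.

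Protocol 7.1 opens its list with "The following are considered contraindications for further administration of the investigational product for an individual subject". The list includes anaphylaxis or a severe related allergic reaction, most thromboembolic events, and clinically significant abnormal bleeding. It does not mention study withdrawal.

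The protocol's own safety section, 10.3.3, plans "Incidence of subjects with AEs leading to discontinuation by SOC and preferred term", without saying whether treatment or study is meant.

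**The concern.** Stopping drug because of an adverse event and leaving the study because of one are different facts about tolerability. The protocol allows the first without the second. If the SAP counts only the second, a report can show no adverse-event discontinuations in an arm where a subject was in fact barred from further dosing.

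Safety and tolerability form the third secondary objective, and protocol 3.3.1 says the study's data will be used to choose doses for a possible phase 3 trial. A reader comparing arms would want to see how many subjects had treatment ended by an adverse event. As planned, they would have to work that out from listings.

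**Working it through.** The point concerns which outputs are defined, so the check is a side-by-side reading, followed by one line of arithmetic for scale. The plan states no figure to reproduce.

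**1. Discontinuation outputs in the SAP**

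| Place | Output | Counted by |
|---|---|---|
| 4.6.1 | Interim AE and SAE summaries | Study discontinuation |
| 9.1 | Disposition, by period and reason | Study discontinuation |
| 11.2 | Dose modification | Dose changes in Treatment Period 2; a permanent stop is not named |
| 11.3 | TEAE overview row and SOC/PT table | Study discontinuation |
| 11.5 | SAE overview row | Study discontinuation |
| 11.6 | SOC/PT table and listing | Study discontinuation |

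No adverse-event output is defined by discontinuation of treatment.

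**2. Does the protocol keep the two events apart?** Section 4.2.1 does so in its wording and in what it has recorded. Section 7.1 speaks only of further dosing. The pregnancy rule in 9.6.6, by contrast, states both that treatment stops and that participation ends. The protocol can therefore be explicit when it means both.

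**3. Trace one subject.** Take a blinded q4wk subject. The last scheduled dose of Treatment Period 1 is at Day 63 (protocol 8.5.2.4) and the period ends at Day 91. Suppose an event listed in protocol 7.1 occurs between those days. Under 7.1 no further dose is given, so the subject is not dosed in Treatment Period 2. The subject attends Day 91 and the follow-up visit as scheduled. SAP 4.1.2 allows subjects to complete the study after Treatment Period 1, so disposition can show a completer. The event enters the adverse event tables, but no summary shows that it ended treatment.

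**4. Do other outputs fill the gap?**
- The adverse event listings carry "serious (yes or no), relationship to treatment (yes or no), outcome, action taken", so the information exists for each event.
- SAP 11.1 summarises the number of SC injections, and the SAP 9.1 listing gives the date of last treatment. Neither gives a reason for stopping.
- Exposure duration in SAP 8.2.8 runs to the Study Completion Visit for subjects who do not enter Treatment Period 2 and for those in it without a dose change. A subject who stops drug mid-period and stays on study therefore keeps accruing exposure.
- Planned dose for compliance (SAP 10.4) is built on that duration, so such a stop could surface as low compliance.

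**5. Scale.** One unidentified subject among n contributes 1/n. For a full blinded arm, 1/8 = 12.5 percentage points (0/8 shown instead of 1/8). For a full FXII/PLG arm of 10, 1/10 = 10 percentage points. No fixed denominator applies in Treatment Period 2, where SAP 11 lets a subject appear under more than one dose.

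**The case against.** The strongest reply is that most treatment stops will be study discontinuations anyway. Protocol 8.5.5 sends subjects who discontinue or are withdrawn to the Week 13 or Week 57 assessments and then to follow-up. The visit schedules repeat this for subjects discontinued from the study, and SAP 8.2.8 places the Study Completion Visit at premature study discontinuation. Neither document describes a visit schedule off drug but on study. This stands as a limit on frequency. It also answers a stronger inference that a reader might draw: that attending those visits makes a stopped subject a completer, so better follow-up means more undercounting. The documents do not support that, because the same visits are the early-exit path.

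Second, the events are reported elsewhere. Protocol 9.1.2 makes systemic thromboembolic events, bleeding judged abnormal and all anaphylaxis serious by rule. They reach the SAE tables. Events matching the standardised queries in SAP 11.4 have their own tables, and related reactions enter the drug-reaction table in 11.7. A reader might infer that thrombotic, bleeding or allergic harms vanish from the report; they do not. A severe allergic reaction outside the anaphylactic-reaction query would have no special-interest table, but it would still be in the general ones. What is missing is the link from event to treatment stop, in a summary.

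Third, the overview items and the listing in protocol 10.3.3 refer to study discontinuation, so the unqualified table title may be shorthand. That is a fair reading. The SAP cannot be shown to depart from the protocol; the terms are simply not aligned.

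Fourth, discontinuation is not among the endpoints listed for the third secondary objective. A reader might take it to be the main tolerability summary for dose selection, but neither document says so.

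**Conclusion.** The gap is real and narrow. SAP 11.6 does not deliver what its heading covers, and no other SAP summary does. A treatment stop for an adverse event that is not also recorded as a study discontinuation goes unidentified as such. No declared endpoint, test or estimate changes.

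The number of subjects affected cannot be derived from the documents and is probably small. With arms this small, even one would be visible in an arm's percentage.

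The conclusion assumes that the separate table shells, which were not available, follow the SAP text. It also assumes that sites record some treatment-only stops, which protocol 4.2.1 permits.

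**What to change.** In SAP 11.6, add a SOC/PT table and a listing of TEAEs leading to discontinuation of study treatment, beside the existing study-discontinuation outputs. Add matching rows to the interim summaries (4.6.1), the TEAE overview (11.3) and the SAE overview (11.5), and a treatment-discontinuation row with reason to disposition (9.1).

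Define the category from the action-taken field together with the treatment-discontinuation reason and date that protocol 4.2.1 requires. The response options for action taken are not shown in either document, so check them against the eCRF first. State whether the category includes a subject who has had every Treatment Period 1 dose and is then not dosed in Treatment Period 2 because of an adverse event.

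Reconcile the wording with protocol 10.3.3, so that treatment and study discontinuation are named distinctly throughout.

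The cost is a few rows, one table and one listing, from data the protocol already collects. Conduct does not change, and no dosing or stopping rule is touched.

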### **11.7 Adverse Drug Reactions**

An adverse drug reaction is defined as either:

- a. A TEAE, including local tolerability events, that began during or within 1 hour of the start of an administration, or
- b. A TEAE reported as causally related to the administration of study treatment, or which the sponsor determined to be causally related to the administration of study treatment, or
- c. A TEAE for which the investigator's causality assessment is missing or indeterminate, or
- d. All TEAEs for which the exposure-adjusted incidence rate in an active treatment arm exceeds the exposure-adjusted incidence rate in the placebo arm by 30% or more, provided the difference in exposure-adjusted incidence rates is 1% or more. This bullet point is only applicable for Treatment Period 1 (blinded and open-label part).

A summary table for adverse drug reactions by SOC and PT will be provided as well as a by-subject listing.

## 11.8 Public Disclosure of Clinical Trials Requirements

To support public disclosure requirements for clinical study, a summary of treatment-related SAEs will be provided.

Additionally, a summary of non-serious TEAEs by SOC and PT will be produced. A summary of the number of subjects with non-serious TEAEs that occurred at a frequency of more than 1%, 2%, 3%, 4%, and 5% will be produced following these steps for each frequency:

- Determine which subjects experienced any non-serious TEAE that occurred at a frequency higher than the frequency of interest.
- From that subset of subjects, sum the subjects who experienced at least one of the non-serious TEAEs that occurred at a frequency higher than the frequency of interest. Do not double count subjects who experienced 2 or more of those non-serious TEAEs.

## 11.9 Pregnancies

If a female subject becomes pregnant, she must discontinue treatment with the investigational product immediately, her participation in the study will be discontinued, and the procedure for discontinuation of a subject will be followed, as described in protocol Section 4.2.

While pregnancy itself is not considered to be an AE or SAE, any pregnancy complication or elective termination of a pregnancy for medical reasons will be recorded as an AE or SAE as described in the protocol. If any subject becomes pregnant while on the study, the information will be included in the narratives and no separate table or listing will be produced.

## 11.10 Clinical Laboratory Evaluations

Laboratory tests will be summarized descriptively by scheduled visit as specified in Section 7. For laboratory test with continuous values, descriptive statistics for the measured values and for change from baseline will be presented. Definition of the baseline assessment can be found in Section 8.2.4. Laboratory tests with categorical values will be summarized by number and percentage of subjects in the respective categories (based on subjects of the Safety population with non-missing values at this time point). Summary tables will be provided for hematology, biochemistry, coagulation, and immunogenicity (inhibitory and non-inhibitory antibodies). All laboratory tests (scheduled and unscheduled) will be listed. The listings will include the variables as specified in Section 7 and in addition the laboratory

test name and unit along with normal range, the sampling date and time, the test result, an assessment whether the result is high (above normal range) or low (below normal range). Any comments to the laboratory test will be provided in a separate listing.

A by-subject listing for laboratory abnormalities will be provided in the same format as the laboratory listings described above but only containing information about abnormal laboratory results.

The number and percentage of subjects who experience antibodies (inhibitory and non-inhibitory) specific to FXIIa will be summarized as a secondary (for subjects with C1-INH HAE) and CCI in this study. Percentages will be based on subjects of the Safety population with non-missing values at each time point.

The number and percentage of subjects with abnormal laboratory values reported as AEs will be summarized by laboratory test and visit and for all laboratory tests combined as a further secondary (for subjects with C1-INH HAE) and CCI. The laboratory findings reported as AEs will be identified through the eCRF. Percentages will be based on subjects of the Safety population with non-missing values at each time point.

The laboratory tests will be presented in the following grouping and sequence as specified in Table 6 of the protocol. The test names used in the TFLs may differ depending on the terminology used by the central laboratory. The test names and units as provided in the laboratory data transfer will be used.

**Hematology:** Hemoglobin, Hematocrit, Erythrocytes (red blood cell count), Mean corpuscular volume, Mean corpuscular hemoglobin, Mean corpuscular hemoglobin concentration, Leukocytes (white blood cell count), Neutrophils (% and absolute), Lymphocytes (% and absolute), Monocytes (% and absolute), Eosinophils (% and absolute), Basophils (% and absolute), and Platelet count.

**Biochemistry:** Sodium, Potassium, Chloride, Carbon dioxide, Albumin, Alkaline phosphatase, Direct bilirubin, Total bilirubin, Aspartate aminotransferase, Total protein, Calcium, Alanine aminotransferase, Creatinine, Phosphate, Blood urea nitrogen, Glucose.

**Coagulation:** CCI [REDACTED]

**Immunogenicity:** Binding antibodies (inhibitory and non-inhibitory) specific to FXIIa antagonist monoclonal antibody.

**Urinalysis:** Bilirubin, Occult blood, Erythrocytes, Glucose, Ketones, Leukocyte esterase, Nitrite, pH, Protein, Specific gravity, Urobilinogen.

